**Table 2. Medical history**

Variable	Intensive blood pressure lowering (N = )	Guideline-recommended blood pressure lowering (N = )	Total (N = )
Previous ischaemic stroke	xxx/xxx xx.x%	xxx/xxx xx.x%	xxx/xxx xx.x%
Previous haemorrhagic stroke	xxx/xxx xx.x%	xxx/xxx xx.x%	xxx/xxx xx.x%
Previous stroke of unknown type	xxx/xxx xx.x%	xxx/xxx xx.x%	xxx/xxx xx.x%
History of coronary heart disease	xxx/xxx xx.x%	xxx/xxx xx.x%	xxx/xxx xx.x%
History of documented atrial fibrillation	xxx/xxx xx.x%	xxx/xxx xx.x%	xxx/xxx xx.x%
History of valvular heart disease	xxx/xxx xx.x%	xxx/xxx xx.x%	xxx/xxx xx.x%
Other heart disease (e.g. heart failure)	xxx/xxx xx.x%	xxx/xxx xx.x%	xxx/xxx xx.x%
History of hypertension	xxx/xxx xx.x%	xxx/xxx xx.x%	xxx/xxx xx.x%
Currently treated hypertension	xxx/xxx xx.x%	xxx/xxx xx.x%	xxx/xxx xx.x%
History of diabetes mellitus	xxx/xxx xx.x%	xxx/xxx xx.x%	xxx/xxx xx.x%
Known coagulation or other haematological disorder	xxx/xxx xx.x%	xxx/xxx xx.x%	xxx/xxx xx.x%
History of liver disease	xxx/xxx xx.x%	xxx/xxx xx.x%	xxx/xxx xx.x%
History of gastrointestinal or urinary bleeding	xxx/xxx xx.x%	xxx/xxx xx.x%	xxx/xxx xx.x%
History of hypercholesterolaemia	xxx/xxx xx.x%	xxx/xxx xx.x%	xxx/xxx xx.x%
Current smoker	xxx/xxx xx.x%	xxx/xxx xx.x%	xxx/xxx xx.x%

**Table 3. Medications at time of admission**

Variable	Intensive BP lowering (N = )	Standard BP lowering (N = )	Total (N = )
Antihypertension drugs used	xxx/xxx xx.x%	xxx/xxx xx.x%	xxx/xxx xx.x%
Type of antihypertension drugs used	xxxx	xxxx	xxxx
ACE or ARB	xxx xx.x%	xxx xx.x%	xxx xx.x%
Diuretic	xxx xx.x%	xxx xx.x%	xxx xx.x%
Calcium channel blocker	xxx xx.x%	xxx xx.x%	xxx xx.x%
Beta-blocker	xxx xx.x%	xxx xx.x%	xxx xx.x%
Other antihypertensive agent	xxx xx.x%	xxx xx.x%	xxx xx.x%
Anticoagulant agent used	xxx/xxx xx.x%	xxx/xxx xx.x%	xxx/xxx xx.x%
Type of anticoagulant agent	xxxx	xxxx	xxxx
Vitamin K antagonist (warfarin, neo-sintrom )	xxx xx.x%	xxx xx.x%	xxx xx.x%
New oral anticoagulant	xxx xx.x%	xxx xx.x%	xxx xx.x%
Apixaban	xxx xx.x%	xxx xx.x%	xxx xx.x%
Dabigaran	xxx xx.x%	xxx xx.x%	xxx xx.x%
Edoxaban	xxx xx.x%	xxx xx.x%	xxx xx.x%
Rivaroxaban	xxx xx.x%	xxx xx.x%	xxx xx.x%
Other anticoagulant	xxx xx.x%	xxx xx.x%	xxx xx.x%
Antiplatelet agent used	xxx/xxx xx.x%	xxx/xxx xx.x%	xxx/xxx xx.x%
Detailed antiplatelet agent	xxxx	xxxx	xxxx
Aspirin	xxx xx.x%	xxx xx.x%	xxx xx.x%
Clopidogrel	xxx xx.x%	xxx xx.x%	xxx xx.x%
Cilostazol	xxx xx.x%	xxx xx.x%	xxx xx.x%
Dipyridamole	xxx xx.x%	xxx xx.x%	xxx xx.x%
Other antiplatelet agent	xxx xx.x%	xxx xx.x%	xxx xx.x%
Blood glucose lowering agents used	xxx/xxx xx.x%	xxx/xxx xx.x%	xxx/xxx xx.x%
Type of glucose lowering agents	xxxx	xxxx	xxxx
Oral agents	xxx xx.x%	xxx xx.x%	xxx xx.x%
Insulin	xxx xx.x%	xxx xx.x%	xxx xx.x%

Variable	Intensive BP lowering (N = )	Standard BP lowering (N = )	Total (N = )
Nitrates used	xxx/xxx xx.x%	xxx/xxx xx.x%	xxx/xxx xx.x%
Statin or other lipid lowering agent	xxx/xxx xx.x%	xxx/xxx xx.x%	xxx/xxx xx.x%

**Table 4. Clinical and BP measures recorded during the first 24 hours**

Variable	Intensive BP lowering (N = )	Standard BP lowering (N = )	Total (N = )
NIHSS Score at 24 hours	xxx	xxx	xxx
Mean (SD)	xxx.x (xxx.x)	xxx.x (xxx.x)	xxx.x (xxx.x)
Median (Q1; Q3)	xxx (xxx; xxx)	xxx (xxx; xxx)	xxx (xxx; xxx)
min max	xxx to xxx	xxx to xxx	xxx to xxx
GCS Score at 24 hours	xxx	xxx	xxx
Mean (SD)	xxx.x (xxx.x)	xxx.x (xxx.x)	xxx.x (xxx.x)
Median (Q1; Q3)	xxx (xxx; xxx)	xxx (xxx; xxx)	xxx (xxx; xxx)
min max	xxx to xxx	xxx to xxx	xxx to xxx
Highest SBP (mmHg)	xxx	xxx	xxx
Mean (SD)	xxx.x (xxx.x)	xxx.x (xxx.x)	xxx.x (xxx.x)
Median (Q1; Q3)	xxx (xxx; xxx)	xxx (xxx; xxx)	xxx (xxx; xxx)
min max	xxx to xxx	xxx to xxx	xxx to xxx
Highest DBP (mmHg)	xxx	xxx	xxx
Mean (SD)	xxx.x (xxx.x)	xxx.x (xxx.x)	xxx.x (xxx.x)
Median (Q1; Q3)	xxx (xxx; xxx)	xxx (xxx; xxx)	xxx (xxx; xxx)
min max	xxx to xxx	xxx to xxx	xxx to xxx
Lowest SBP (mmHg)	xxx	xxx	xxx
Mean (SD)	xxx.x (xxx.x)	xxx.x (xxx.x)	xxx.x (xxx.x)
Median (Q1; Q3)	xxx (xxx; xxx)	xxx (xxx; xxx)	xxx (xxx; xxx)
min max	xxx to xxx	xxx to xxx	xxx to xxx
Lowest DBP (mmHg)	xxx	xxx	xxx
Mean (SD)	xxx.x (xxx.x)	xxx.x (xxx.x)	xxx.x (xxx.x)
Median (Q1; Q3)	xxx (xxx; xxx)	xxx (xxx; xxx)	xxx (xxx; xxx)
min max	xxx to xxx	xxx to xxx	xxx to xxx

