6.7 Treatments Allocation

Attending clinicians are required to consider their level of clinical uncertainty over the balance of potential benefits and risks pertaining to the level of BP control in each particular patient. Investigators are encouraged to adhere to study protocols, provide active care, but are free to modify a patient's treatment as required according to clinical judgment.

Intensive BP lowering group

The aim is to achieve a systolic BP level of <120mmHg within 1 hour after randomisation and to maintain this BP level for the next 72 hours (or until hospital discharge or death if this should occur earlier). A standardised intravenous (i.v.) BP lowering regimen using locally available and approved i.v. BP lowering agents will be used, commenced immediately after randomisation in either the catheter lab or a high dependency area (e.g. acute stroke or neurointensive care unit) as is usual for patients receiving MT.

BP lowering will be titrated by repeat i.v. bolus or infusion, with a systolic BP of 100 mmHg being the safety threshold for cessation of therapy. It is anticipated that i.v. agents will be required for at least the first several hours in most cases but the timing of switch to oral BP lowering agents will be at the discretion of the responsible clinician according to BP control and patient status. It is also expected that i.v. therapy will continue to be required during the initiation of oral antihypertensive therapy, to maintain the systolic BP levels 100-120 mmHg.

When administering BP lowering treatment, care is required to ensure that severe hypotension is avoided in patients by checking first for potential dehydration and providing intravenous fluids.

Since the study seeks to address the impact of BP lowering and not a specific agent, and to ensure the trial result is maximally generalizable to existing routine practice, some flexibility is allowed in the use of locally available i.v. agents (e.g. urapidil, hydralazine, metoprolol, clevipipine), but all other aspects treatment are standardized across sites. Patients on prior oral BP lowering agents should have this continued if possible and antihypertensive therapy prescribed when patients are clinically stable as per guidelines for secondary stroke prevention. Investigators are encouraged to adhere to study protocols, provide active care, but are free to modify a patient's treatment as required according to clinical judgment.

I.v. treatment protocol

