7.2.3 Monitoring of SAEs

The CCC will closely monitor all SAEs for any relationship to the study procedures and protocol and clustering of events at a particular site. The protocol will be amended or the study will be stopped earlier if an excess of particular SAEs appear to be protocol related, for example severe hypotensive events requiring emergency treatment in the intensive BP lowering group. In addition, the CCC will submit all SAEs to the independent Data Safety Monitoring Board (DSMB) for review outside of the planned interim analysis meetings.

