### 2.3.2 Study treatment

**Intensive BP lowering group:** to commence intravenous BP lowering therapy immediately after randomisation to the intervention group. The SBP target is <120 mmHg within 1 hour, and to maintain this level for at least 72 hours (or hospital discharge, if earlier).

**Control group:** the patient allocated to this group will receive a higher BP target strategy to maintain SBP level 140-180 mmHg after the EVT procedure. BP lowering treatment can be given only for a SBP level  $>$ 150 mmHg, if required to achieve the target of  $\geq$ 140 mmHg.

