### **3.6 BP management**

BP measurements collected during the first 24 hours will be summarised using descriptive and longitudinal mean plots. The overall mean per treatment arm, and overall difference (and 95% confidence interval [CI]) between treatment arms, will be calculated using a repeated-measure linear mixed model with a fixed effect of treatment, a fixed categorical effect of time, a fixed interaction between treatment and time, and a repeated patient effect (to model within-patient correlations assuming a compound-symmetry structure). We will adjust for stratification variables by including a random site effect, a fixed effect for time from onset to recanalisation (<6 vs ≥ 6 hours), and a fixed effect for baseline NIHSS (<17 vs ≥ 17). Estimates will be weighted to reflect the unequal spacing between measurements.

BP lowering medications administered during the first 24 hours, and during days 2-7, will be described as the number and proportion of participants receiving each medication. This will include method of intravenous (iv) administration as well as the number of different iv or oral medications (0, 1, 2, ≥3) taken. No statistical test will be performed.

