### **3.8.8 Serious adverse events (SAEs)**

SAEs will be summarised as the number of events as well as the number and proportion of patients experiencing at least one SAE event. This will be done overall and by category of event according to Medical Dictionary for Regulatory Activities (MeDRA) system organ classes and preferred terms. The overall proportion of patients with SAEs in the intervention and control arms will be compared using logistic regression as in the binary analysis of mRS (see Section 3.8.1). Primary and underlying causes of deaths will be summarised by treatment arm with no formal test.

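### The SAP never counts patients who reach the protocol's 100 mmHg systolic safety threshold, and its lowest-SBP summary stops at 24 of the 72 treated hours

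*SAP*

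**What the plan says.** Protocol 6.7 titrates the intensive arm "with a systolic BP of 100 mmHg being the safety threshold for cessation of therapy". Appendices 1A to 1D put the cessation point at an SBP of 100 mmHg or less. The target is to be reached within an hour, and the aim is then "to maintain this BP level for the next 72 hours"; SAP 2.3.2 likewise says "to maintain this level for at least 72 hours", in both cases ending at discharge if earlier.

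Protocol 4.2.3 warns that intensive lowering could worsen ischaemia, and its hypothesis is better function without other harms. Protocol 7.2.3 illustrates an excess of SAEs that could lead to amending or stopping the study: "for example severe hypotensive events requiring emergency treatment in the intensive BP lowering group".

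On analysis, SAP 3.6 says: "BP measurements collected during the first 24 hours will be summarised using descriptive and longitudinal mean plots". Table 4 gives the row "Lowest SBP (mmHg") by arm as mean (SD), median (quartiles) and range, for the first 24 hours. Table 8 gives n and mean (SD) of SBP and DBP by arm at each time point to the evening of Day 7. For SAEs, section 3.8.8 says: "This will be done overall and by category of event according to Medical Dictionary for Regulatory Activities". Table 15 follows this with events and patients per preferred term by arm, and Listing 2 lists each SAE. The only formal test is on any SAE: "The overall proportion of patients with SAEs in the intervention and control arms will be compared using logistic regression".

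**The concern.** Low blood pressure is the most direct harm of a target below 120 mmHg, and the protocol supplies its own marker for it. If intensive lowering proves harmful, readers will ask first how many patients reached 100 mmHg. If it proves beneficial, they will want the same number as its safety cost. Followed as written, the plan produces that number for neither the first 24 hours nor the full treated period. A cut-off chosen after the results are known would be less convincing than one fixed now.

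**Working it through.** There is no sample-size or alpha figure to reproduce. The check is what each planned output can and cannot show.

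1. **Coverage of the treated period.** Protocol 6.10.5 (Form C) schedules BP every 15 minutes for 1 hour (4 readings), hourly for 5 hours (5), then 6-hourly to 24 hours (3): 4 + 5 + 3 = 12. Protocol Table 2 gives 12-hourly readings after Day 1: 48/12 = 4 between 24 and 72 hours. Table 4 therefore covers 24/72 = 33% of treated time and 12/16 = 75% of scheduled readings. The other 48 hours (67%) and 4 readings (25%) have no minimum or threshold summary.

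2. **What Table 4 leaves open.** Take half of 2257, about 1128 patients, in the intensive arm. Without any distributional assumption:
   - lower quartile above 100 and minimum at or below 100: from 1 up to about 0.25 × 1128 = 282 patients at or below 100;
   - lower quartile at or below 100 and median above it: about 282 to 564.

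   The maintenance range in the appendices is 100-120 mmHg, so the threshold lies at the edge of the intended range, where some patients' lowest readings can be expected.

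3. **What Table 8 leaves open.** The documents give no on-treatment SD, so this is illustration only. Assume normal SBP with mean 115-125 and SD 10-15 mmHg. The share below 100 at one time point is Φ((100 − mean)/SD): 0.6% at mean 125, SD 10; 4.8% at mean 120, SD 12; 15.9% at mean 115, SD 15. Even if that share were known exactly at all four readings from 24 to 72 hours, the share of patients *ever* below 100 would be bounded only between p (the same patients each time) and 4p (different patients each time). For p = 4.8% that is 4.8% to 19.2%, or about 54 to 217 of 1128 patients, if all still have readings. Separate time-point summaries cannot give a per-patient count.

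4. **What the SAE tables add.** The schedule in Protocol Table 2 collects SAEs and has no row for non-serious events. Hypotension meeting the SAE definition will appear in Table 15 by arm. A crossing that does not become an SAE is counted nowhere.

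5. **Comparability of the minimum in Table 4.** Protocol 6.10.5 asks for extra readings 5 and 15 minutes after each i.v. bolus. The intensive-arm charts (Appendices 1A to 1E) ask for readings every 5 minutes during active treatment, then every 15 minutes for 1 hour (4), every 30 minutes for 5 hours (10) and hourly to 24 hours (18): 4 + 10 + 18 = 32, against 12 on Form C. Appendix 1G gives no such schedule for controls. The SAP does not say which readings feed Table 4. If all recorded values do, the intensive arm has more chances to record a low one.

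**The case against.** A reader might infer that hypotension goes unreported by arm, or that the SAP looks only at any SAE. The documents do not support that. SAEs are tabulated by preferred term by arm and listed individually, Protocol 10.2 also plans to tabulate specific SAEs and discontinuation due to SAEs, and the hypotensive events named in Protocol 7.2.3 are themselves an example of SAEs. BP after 24 hours is not ignored either, since Table 8 runs to Day 7. This stands, and it limits the point to threshold crossings and non-serious hypotension.

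It is also tempting to say that one reported mean fits very different tails. With normal minima of mean 112 mmHg, the share below 100 is 2.3% at SD 6 and 21.2% at SD 15, or 26 to 239 patients. But Table 4 reports the SD and quartiles beside the mean, so under that same model the share would be fixed, and the mean of 112 has no basis in the documents. The quartile bounds above are the sounder argument.

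Other routes to the information exist: the seven-day BP chart, the deviation form, the non-compliance rows of Table 17, DSMB review of BP differences, and a later paper on BP parameters (SAP Appendix 3). None is a planned count by arm in the main report. Stopping treatment at the threshold also follows the protocol, so it need not be recorded as non-compliance.

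Finally, 100 mmHg is a cessation threshold for one arm, not a stated definition of hypotension. With a control target of 140-180 mmHg, control events may be very few. That is a fair reason not to rely on a random-site logistic odds ratio. It does not argue against reporting counts.

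**Conclusion.** The point holds in limited form. The SAP plans no count of patients reaching the protocol's own safety threshold, its lowest-SBP summary omits 48 of 72 treated hours, and hypotension is visible by arm only as a coded SAE. The gap in time is 67%, but in scheduled readings it is about 25%. How many patients crossed cannot be recovered from the planned tables except within wide bounds. The bias in Table 4 from extra intensive-arm readings is possible, not established, because the SAP does not state the source of the readings. The primary outcome, its test and the error rate are untouched, and the data to answer the question are already scheduled for collection. This is an inexpensive improvement that should be made. It is not a flaw that undermines the trial.

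**What to change.** In SAP 3.6 and 3.8.8, with matching rows in Tables 4 and 8, for reporting only:

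- Give n (%) per arm with any SBP ≤100 mmHg, the form used in Appendices 1A to 1D, and also <100 mmHg. Use only the scheduled readings common to both arms (Form C times to 24 hours, then 12-hourly), separately for 0-24 h and 24-72 h.
- Use all randomised patients, and state how many have a reading in each window, since discharge or death may come before 72 hours. The population must be stated because SAP 3.2 bases safety on the ITT population, while the opening of 3.8 applies the efficacy set to the analyses that follow.
- Extend lowest SBP to 72 hours on the same readings, and reconcile the 24-hour text of 3.6 with Table 8, which runs to Day 7.
- Report a risk difference with 95% CI. Add the logistic model of 3.8.1 only if control-arm events are enough for a stable fit, with the minimum number fixed in advance.
- Show hypotension-coded SAEs as a named row in Table 15.

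The cost is a few table rows and short runs on data already collected. The stated downside is that after 24 hours readings are 12-hourly, so the count is a lower bound; leaving out post-bolus checks also misses brief dips, in exchange for comparability between arms. The change proposes no dose, target or clinical rule.

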**Table 5. Antihypertensive treatments administered during the first 24 hours**

Variable	Intensive BP lowering (N = )	Guideline-recommended BP lowering (N = )	Total (N = )
Any BP medication taken	xxx/xxx xx.x%	xxx/xxx xx.x%	xxx/xxx xx.x%
IV hypertensive treatment	xxx/xxx xx.x%	xxx/xxx xx.x%	xxx/xxx xx.x%
Types of IV hypertensive treatment	xxx	xxx	xxx
Bolus	xxx xx.x%	xxx xx.x%	xxx xx.x%
Infusion	xxx xx.x%	xxx xx.x%	xxx xx.x%
Type of IV antihypertensive treatment	xxx	xxx	xxx
<treatment 1>	xxx xx.x%	xxx xx.x%	xxx xx.x%
<treatment 2>	xxx xx.x%	xxx xx.x%	xxx xx.x%
Etc. in decreasing order of frequency	xxx xx.x%	xxx xx.x%	xxx xx.x%

**Table 6. Management care administered until Day 7**

Variable	Intensive blood pressure lowering (N = )	Guideline-recommended blood pressure lowering (N = )	Total (N = )
Intubation and ventilation	xxx/xxx xx.x%	xxx/xxx xx.x%	xxx/xxx xx.x%
Fever	xxx/xxx xx.x%	xxx/xxx xx.x%	xxx/xxx xx.x%
Fever treated	xxx/xxx xx.x%	xxx/xxx xx.x%	xxx/xxx xx.x%
Assisted feeding	xxx/xxx xx.x%	xxx/xxx xx.x%	xxx/xxx xx.x%
Mobilised by physiotherapist/occupational therapist	xxx/xxx xx.x%	xxx/xxx xx.x%	xxx/xxx xx.x%
Compression stockings used	xxx/xxx xx.x%	xxx/xxx xx.x%	xxx/xxx xx.x%
Subcutaneous heparin or heparinoids administered	xxx/xxx xx.x%	xxx/xxx xx.x%	xxx/xxx xx.x%
Intravenous heparin administered	xxx/xxx xx.x%	xxx/xxx xx.x%	xxx/xxx xx.x%
Glycaemic control given	xxx/xxx xx.x%	xxx/xxx xx.x%	xxx/xxx xx.x%
Aspirin or other anti-platelet agent administered	xxx/xxx xx.x%	xxx/xxx xx.x%	xxx/xxx xx.x%
Mannitol used	xxx/xxx xx.x%	xxx/xxx xx.x%	xxx/xxx xx.x%
Intravenous traditional Chinese medicine administered	xxx/xxx xx.x%	xxx/xxx xx.x%	xxx/xxx xx.x%
Intravenous steroids administered	xxx/xxx xx.x%	xxx/xxx xx.x%	xxx/xxx xx.x%
Hemicraniectomy performed	xxx/xxx xx.x%	xxx/xxx xx.x%	xxx/xxx xx.x%
Acute Stroke Unit admission	xxx/xxx xx.x%	xxx/xxx xx.x%	xxx/xxx xx.x%
Intensive care unit admission	xxx/xxx xx.x%	xxx/xxx xx.x%	xxx/xxx xx.x%
Requirement for any form of renal dialysis	xxx/xxx xx.x%	xxx/xxx xx.x%	xxx/xxx xx.x%
Clinical decision made to withdraw 'active' care	xxx/xxx xx.x%	xxx/xxx xx.x%	xxx/xxx xx.x%
Rehabilitation therapy given	xxx/xxx xx.x%	xxx/xxx xx.x%	xxx/xxx xx.x%

**Table 7. Details of hypertensive treatments between Days 2 and 7**

Variable	Intensive BP lowering (N = )	Standard BP lowering (N = )	Total (N = )
IV antihypertensive treatment	xxx/xxx xx.x%	xxx/xxx xx.x%	xxx/xxx xx.x%
Type of IV antihypertensive treatment	xxx	xxx	xxx
<treatment 1>	xxx xx.x%	xxx xx.x%	xxx xx.x%
<treatment 2>	xxx xx.x%	xxx xx.x%	xxx xx.x%
Etc. in decreasing order of frequency	xxx xx.x%	xxx xx.x%	xxx xx.x%
Oral hypertensive treatment	xxx/xxx xx.x%	xxx/xxx xx.x%	xxx/xxx xx.x%
Type of oral antihypertensive treatment	xxx	xxx	xxx
<treatment 1>	xxx xx.x%	xxx xx.x%	xxx xx.x%
<treatment 2>	xxx xx.x%	xxx xx.x%	xxx xx.x%
Etc. in decreasing order of frequency	xxx xx.x%	xxx xx.x%	xxx xx.x%

**Table 8. Descriptive analysis of blood pressure**

Variable / Timepoint	Intensive BP lowering (N = )	Standard BP lowering (N = )	Total (N = )
SBP (n mean (SD))			
Randomisation	xxx xxx.x (xx.x)	xxx xxx.x (xx.x)	xxx xxx.x (xx.x)
15 min	xxx xxx.x (xx.x)	xxx xxx.x (xx.x)	xxx xxx.x (xx.x)
30 min	xxx xxx.x (xx.x)	xxx xxx.x (xx.x)	xxx xxx.x (xx.x)
45 min	xxx xxx.x (xx.x)	xxx xxx.x (xx.x)	xxx xxx.x (xx.x)
1 hr	xxx xxx.x (xx.x)	xxx xxx.x (xx.x)	xxx xxx.x (xx.x)
2 hr	xxx xxx.x (xx.x)	xxx xxx.x (xx.x)	xxx xxx.x (xx.x)
Etc.			
Day 7, pm	xxx xxx.x (xx.x)	xxx xxx.x (xx.x)	xxx xxx.x (xx.x)
DBP (n mean (SD))			
Randomisation	xxx xxx.x (xx.x)	xxx xxx.x (xx.x)	xxx xxx.x (xx.x)
15 min	xxx xxx.x (xx.x)	xxx xxx.x (xx.x)	xxx xxx.x (xx.x)
30 min	xxx xxx.x (xx.x)	xxx xxx.x (xx.x)	xxx xxx.x (xx.x)
45 min	xxx xxx.x (xx.x)	xxx xxx.x (xx.x)	xxx xxx.x (xx.x)
1 hr	xxx xxx.x (xx.x)	xxx xxx.x (xx.x)	xxx xxx.x (xx.x)
2 hr	xxx xxx.x (xx.x)	xxx xxx.x (xx.x)	xxx xxx.x (xx.x)
Etc.			
Day 7, pm	xxx xxx.x (xx.x)	xxx xxx.x (xx.x)	xxx xxx.x (xx.x)

**Table 9. Descriptive analysis of mRS**

Timepoint / Score	Intensive BP lowering (N = )	Standard BP lowering (N = )	Total (N = )
Baseline	N=xxx	N=xxx	N=xxx
0	xx (xx.x%)	xx (xx.x%)	xx (xx.x%)
1	xx (xx.x%)	xx (xx.x%)	xx (xx.x%)
2	xx (xx.x%)	xx (xx.x%)	xx (xx.x%)
3	xx (xx.x%)	xx (xx.x%)	xx (xx.x%)
4	xx (xx.x%)	xx (xx.x%)	xx (xx.x%)
5	xx (xx.x%)	xx (xx.x%)	xx (xx.x%)
6	xx (xx.x%)	xx (xx.x%)	xx (xx.x%)
Day 7	N=xxx	N=xxx	N=xxx
0	xx (xx.x%)	xx (xx.x%)	xx (xx.x%)
1	xx (xx.x%)	xx (xx.x%)	xx (xx.x%)
2	xx (xx.x%)	xx (xx.x%)	xx (xx.x%)
3	xx (xx.x%)	xx (xx.x%)	xx (xx.x%)
4	xx (xx.x%)	xx (xx.x%)	xx (xx.x%)
5	xx (xx.x%)	xx (xx.x%)	xx (xx.x%)
6	xx (xx.x%)	xx (xx.x%)	xx (xx.x%)
Day 90	N=xxx	N=xxx	N=xxx
0	xx (xx.x%)	xx (xx.x%)	xx (xx.x%)
1	xx (xx.x%)	xx (xx.x%)	xx (xx.x%)
2	xx (xx.x%)	xx (xx.x%)	xx (xx.x%)
3	xx (xx.x%)	xx (xx.x%)	xx (xx.x%)
4	xx (xx.x%)	xx (xx.x%)	xx (xx.x%)
5	xx (xx.x%)	xx (xx.x%)	xx (xx.x%)
6	xx (xx.x%)	xx (xx.x%)	xx (xx.x%)

**Table 10. Descriptive analysis of NIHSS**

	Intensive BP lowering (N = )	Guideline- recommended BP lowering (N = )	Total (N = )
Baseline	N=xxx	N=xxx	N=xxx
< 5	xx (xx.x%)	xx (xx.x%)	xx (xx.x%)
5 – 9	xx (xx.x%)	xx (xx.x%)	xx (xx.x%)
10 – 14	xx (xx.x%)	xx (xx.x%)	xx (xx.x%)
15 – 19	xx (xx.x%)	xx (xx.x%)	xx (xx.x%)
20 – 24	xx (xx.x%)	xx (xx.x%)	xx (xx.x%)
≥ 25	xx (xx.x%)	xx (xx.x%)	xx (xx.x%)
Death	xx (xx.x%)	xx (xx.x%)	xx (xx.x%)
Mean (SD)	xx (xx.x)	xx (xx.x)	xx (xx.x)
Median (Q1 – Q2)	xx (xx – xx)	xx (xx – xx)	xx (xx – xx)
Min - Max	xx – xx	xx – xx	xx – xx
Day 7	N=xxx	N=xxx	N=xxx
< 5	xx (xx.x%)	xx (xx.x%)	xx (xx.x%)
5 – 9	xx (xx.x%)	xx (xx.x%)	xx (xx.x%)
10 – 14	xx (xx.x%)	xx (xx.x%)	xx (xx.x%)
15 – 19	xx (xx.x%)	xx (xx.x%)	xx (xx.x%)
20 – 24	xx (xx.x%)	xx (xx.x%)	xx (xx.x%)
≥ 25	xx (xx.x%)	xx (xx.x%)	xx (xx.x%)
Death	xx (xx.x%)	xx (xx.x%)	xx (xx.x%)
Mean (SD)	xx (xx.x)	xx (xx.x)	xx (xx.x)
Median (Q1 – Q2)	xx (xx – xx)	xx (xx – xx)	xx (xx – xx)
Min - Max	xx – xx	xx – xx	xx – xx

